### Bayesian Sensitivity Analyses

Sensitivity analyses will be conducted in both ITT and PPA populations to assess alternative definitions to degree of study drug exposure. Specifically, the Bayesian cumulative logistic regression with HFD-90 outcome and analysis populations will be conducted for pooling across study drug dose and borrowing across pre-operative duration of study drug. The Bayesian ordinal logistic model will be the same as described above except with the following modifications to  $\theta_{t,d}$

$$\theta_{t(j),d(j)} = \beta_t + \kappa_d \quad for \ t = 2,3,4 \ and \ d = 1,2,3.$$

Here,  $\beta_t$  is the log-odds ratio due to the dose and  $\kappa_d$  is the log-odds ratio due to the duration. Under the sensitivity analysis where we pool across all active doses we assume  $\beta_t = 0$  for all active doses,  $t = 2:4$ .

Under the sensitivity analysis, we assume a hierarchical distribution for the pre-op duration effects centered around a common mean so there is borrowing of information across pre-op durations:

$$\kappa_d \sim N(\mu_k, .5^2) \text{ for } d = 1,2,3;$$

$$\mu_k \sim N(0,1).$$

### *Frequentist Sensitivity Analyses*

In addition, sensitivity analyses will be conducted in which frequentist regression models are used in place of the Bayesian cumulative logistic regression and without borrowing across groups. For these analyses, we will assess HFD-90 by 4 definitions of treatment arms based on the intervention, on both the ITT and PPA populations:

1. Treated (any duration and/or dose combined to a single group) vs. placebo
2. Metformin 1500mg ER vs. Metformin 1000mg ER vs. Metformin 500mg ER vs. Placebo (each pooled across duration)
3. Long Metformin (>90 days) vs. Medium Metformin (29-90 days) vs. Short Metformin (7-28 days) vs. Placebo (each pooled across the 3 doses of study drug)
4. Placebo vs. 500mg and 7-28 day duration vs. all other treatment combinations

For each of these definitions, we will apply two approaches:

1. A frequentist proportional odds model for the cumulative odds of 90-day HFD being less than or equal to a cut point  $c$ , where  $c = -1, \dots, 89$ , as described in the primary Bayesian analysis above. The treatment effect will be estimated, adjusting for surgical strata and duration as covariates.
2. A Mann-Whitney U test with ties for differences in HFD-90 by treatment arm. Test statistics and p-values will be presented. We will report death as a dichotomous outcome (vs. no death) and, among survivors, HFD-90 as a continuous outcome, as outlined in Section 11.

In the logistic regression model, the model structure will be as follows:

$$y_i = \text{logit}(\beta_0 + \beta_i * \text{tx arm}_i + \varepsilon_i);$$

Where:

$y_i$ : Outcome (HFD-90 = 90 vs.  $\neq 90$ ) for subject i

$\beta_0$  = Coefficient for intercept (for odds of outcome for placebo (reference) group)

$\beta_i$  = Coefficient(s) for treatment(s) vs. placebo

$\varepsilon_i$  = Residual Error for Subject I (i.e. Subject-level random/residual error)

### 13.1.1. Proportional Odds Assumption

The proportional odds assumption of the treatment effect from the cumulative logistic regression model can be viewed as an average of the individual ORs resulting from dichotomizing at each of the possible cut points of HFD-90. The proportional odds assumption is not required to obtain the average OR estimate; however, this estimate may be a poor summary of treatment effect in the presence of large deviations from proportionality. The degree to which the proportionality assumption is valid will be assessed through visual inspection of the cumulative probability curve across all HFD-90 values within each active treatment arm (when pooling pre-op duration) and within each pre-op duration (when pool active doses) will be compared to the cumulative probability curve under the placebo group. Additionally, we will evaluate the individual ORs under each dichotomization of HFD-90 compared to the overall average OR under the cumulative logistic regression model.

## 13.2. Analytic Approach for Secondary Endpoints

### *Primary Analysis*

The analysis of secondary endpoints will be conducted with Frequentist methods using unadjusted linear regression, logistic regression, and Cox models for continuous, dichotomous, and time-to-even secondary endpoints, respectively on both the ITT and PPA populations. Secondary endpoints are described in section 9.2 above. Treatment arms will be pooled across all durations and doses to form treated vs. placebo groups, with the placebo group used as the reference category in all analyses. There will be no adjustment for covariates, other than treatment arm.

The model structures will mimic the approach used in the frequentist analysis of the primary endpoint above. Specifically:

Linear regression:

$$y_i = \beta_0 + \beta_i * tx\_arm_i + \varepsilon_i;$$

Logistic regression:

$$y_i = \text{logit}(\beta_0 + \beta_i * tx\_arm_i + \varepsilon_i);$$

Cox Regression:

$$h(t|x_i) = h_0(t) * \exp(\beta_i * tx\_arm_i);$$

Where:

$y_i$  or  $h(t|x_i)$ : Secondary outcome of interest for subject  $i$

$\beta_0$  or  $h_0(t)$  = Coefficient for intercept or baseline hazard estimate

$\beta_i$  = Coefficient(s) for treatment(s) vs. placebo

$\varepsilon_i$  = Residual Error for Subject  $i$  (i.e. Subject-level random/residual error)

Statistical significance will be defined as an unadjusted  $p < 0.025$ . For all models, outputs will be reported using standard conventions and will include regression coefficients, standard deviations, confidence intervals, test statistics, and p-values, as relevant to each model. Model outputs will be reported both graphically and in tables, as described in sections 10 and 13.10.

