Outcome measures	
Primary REMAP endpoint: hospital free days at day 90 after the surgical encounter
 
Secondary REMAP endpoints refer to Core Protocol
 
Secondary domain endpoints:
 
 1. Gastrointestinal distress causing discontinuation of the medication 2. Lactic acidosis 3. Hepatic dysfunction 
Serious Adverse Events (SAE) as defined in CORE protocol

TABLE OF CONTENTS

1. ABBREVIATIONS	6
2. PROTOCOL APPENDIX STRUCTURE	7
3. Metformin DOMAIN-SPECIFIC APPENDIX VERSION	7
3.1. Version History.....	7
4. Metformin DOMAIN GOVERNANCE.....	8
4.1. Domain Members	8
4.2. Contact Details.....	10
5. Metformin DOMAIN-SPECIFIC WORKING GROUP AUTHORIZATION	11
6. BACKGROUND AND RATIONALE	11
6.1. Domain Definition	11
6.2. Domain-specific Background	11
6.2.1. Guideline Recommended Use of Metformin and Potential Applications	12
6.2.2. Metformin Mechanisms of Action.....	13
6.2.3. Association of Metformin with Longevity in Small Clinical Trials	13
6.2.4. Metformin Safety Profile	13
7. DOMAIN OBJECTIVES	14
8. TRIAL DESIGN	15
8.1. Population.....	15
8.2. Eligibility Criteria	15
8.2.1. Inclusion Criteria for this Domain	15
8.2.2. Exclusion Criteria from this Domain	15
8.3. Interventions	16
8.3.1. Research Testing	16
8.3.2. Study Drug Intervention.....	16
8.3.3. Timing of Initiation of Intervention.....	17
8.3.4. Duration of Administration of Study Drug	17
8.3.5. Temporary Suspension of Study Drug.....	17
8.3.6. Suspension of Study Drug at the Direction of the Treating Clinician.....	17
8.3.7. Collection of Blood Samples	18
8.3.8. Collection of Samples for Microbiome Sub-study	18
8.3.9. Collection of questionnaires	19

8.3.10. Muscle Biopsy Sub-Study	21
8.4. Endpoints	23
8.4.1. Primary Endpoint	23
8.4.2. Secondary Endpoints.....	23
9. TRIAL CONDUCT	24
9.1. Domain-specific Data Collection	24
9.1.1. Clinical Data Collection	24
9.2. Criteria for Discontinuation	24
9.3. Blinding	24
9.3.1. Blinding	24
9.3.2. Unblinding.....	24
10. STATISTICAL CONSIDERATIONS.....	24
10.1. Domain-specific Stopping Rules.....	24
10.2. Strata.....	25
10.3. Timing of Revealing of Randomization Status	25
10.4. Interactions with Interventions in Other Domains	25
10.5. Post-trial Sub-groups.....	26
11. ETHICAL CONSIDERATIONS	26
11.1. Data Safety and Monitoring Board	26
11.2. Potential Domain-specific Adverse Events	26
11.3. Domain-specific Consent Issues.....	26
12. GOVERNANCE ISSUES	27
12.1. Funding of Domain.....	27

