8.3.2. Study Drug Intervention

Patients will be randomly assigned to intention to receive one of the following study interventions.

- Placebo
- Metformin 500mg ER
- Metformin 1000mg ER
- Metformin 1500mg ER

The dosing of and route of administration of metformin are not specified in the protocol but the following guidance is provided:

- Doses will be oral
- Subjects will be instructed to take a dose once daily and complete all dispensed medication from the provided pill bottle

Metformin should be discontinued if the patient experiences a serious adverse event (SAE) that is thought to be related to the study drug and may be discontinued at the discretion of the treating clinician if continued treatment is not in the best interest of the patient.

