8.3.3. Timing of Initiation of Intervention

The intervention is to begin on the day following the evaluation of the eligible and consented subject at the pre-operative clinic/surgeon's office. Daily oral doses will continue through the hospital admission for elective surgery. For patients without side effects, dosing will continue daily for 90 days after the surgical encounter.

Patients will be contacted between the pre-operative clinic/surgeon's office visit and surgery to evaluate study drug compliance as well as any adverse events associated with the study drug.

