### 9.2. Secondary Endpoints

Secondary domain-specific outcome measures include information about EHR based alerts reported during the index elective surgical admission, perioperative outcomes, and surgical outcomes.

Specifically, they include:

- Perioperative outcomes (enrollment to postoperative 90 days)
  - Gastrointestinal intolerance (dichotomous; present/absent)
  - SAE as defined in Core Protocol (mild, moderate, severe, life threatening/disabling; adjudicated as related, possibly related, unrelated)

- Surgical outcomes
  - Index admission
    - Postoperative intensive care unit (ICU) admission (dichotomous; any admission/none)
    - ICU length of stay (LOS; continuous, days)
    - Hospital LOS (continuous, days)
    - Discharge disposition (categorical; Home, SNF/LTAC, Death/Hospice)
    - In-hospital mortality (dichotomous; yes/no)
  - 30-day outcomes
    - Organ failure free days (i.e., vasopressor exposure, hemodialysis, or mechanical ventilation; continuous, days)
    - Surgical site infection, as defined by NSQIP and the CDC (categorical)
    - Surgical site occurrence, as defined by Ventral Hernia Working Group (categorical)
  - 90-day outcomes
    - Reoperation/reintervention, both incidence and total number (dichotomous, time to event; any/none and continuous, number)
    - Readmission (dichotomous, time to event; any/none, days)
    - Venous thromboembolic events including deep vein thrombosis and pulmonary embolus after surgery (dichotomous, time to event; any/none, days)
    - Mortality (dichotomous, time to event; yes/no, days)

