## 11. DESCRIPTIVE STATISTICS

All demographics, baseline characteristics, and perioperative information will be summarized for all randomized participants, the ITT, and PPA analysis populations. Summaries will be presented by treatment group (metformin vs placebo), by treatment and dosage group, and by surgical strata. Data abstracted prospectively throughout the trial, data within trial reporting documentation, as well as data abstracted from the electronic health record will be recorded and included in the summaries. Baseline demographics and characteristics will include age at randomization, sex at birth, race, ethnicity, body mass index, frailty status as measured by the Risk Analysis Index, smoking status, Charlson Comorbidity Index, occurrence of comorbid conditions, preoperative medications, ASA class, surgical strata, and year of randomization. All analyses will be completed both in the ITT and PPA populations.

Primary and supplemental tables will include the following populations:

- 1- By primary treatment group (Metformin vs placebo)
- 2- By primary treatment group, separated by dose
- 3- By primary treatment group, separated by preoperative duration and dose
- 4- By surgical strata

All endpoints will be modeled following a standard convention based upon the frequency of the events. For interventions with <10 subjects, we will summarize outcomes with No. (%) without modeling due to the small sample size. All analysis will be completed both in the ITT and PPA populations.

- 1- Ordinal endpoints will be summarized by the number and cumulative frequency of each outcome. The 25th, 50th, and 75th percentiles will be summarized.
- 2- Dichotomous endpoints will be summarized by the proportion in each category.
- 3- Composite endpoints will be summarized overall and for each component individually.
- 4- Time-to-event outcomes will be summarized by the 2.5th, 10th, 25th, 50th, 75th, 90th, and 97.5th percentiles from the Kaplan-Meier estimates, as available.
- 5- Continuous endpoints will be summarized by the mean, standard deviation or median, interquartile range (IQR) pending the distribution of the data.

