## 12. TREATMENT DELIVERY

Following randomization, study drug was either provided to the subjects in clinic or study drug was mailed directly to their home. Study drug compliance was monitored at the postoperative 90-day interaction with the study team. At this time, participants who discontinued their medications were determined not adherent and those who continued were adherent. In addition, if patients reported early termination or non-adherence to study drug, this was recorded by study coordinators and reported.

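### GI intolerance and SAEs are analysed in a per-protocol population that leaves out patients who stopped drug because of those events, and the SAP does not say which population supports tolerability conclusions

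*SAP*

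**What the plan says.** SAP section 13.2 fits linear, logistic and Cox models to continuous, dichotomous and time-to-event "secondary endpoints, respectively on both the ITT and PPA populations". SAP section 11 is broader: "All analysis will be completed both in the ITT and PPA populations". SAP section 9.2 lists GI intolerance (yes/no) and SAEs (graded, and adjudicated for relatedness) among the secondary endpoints, both counted from enrolment to postoperative day 90.

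SAP section 8 limits the PPA to patients who completed their allocated treatment, as confirmed verbally at the 90-day contact. Section 12 applies this without regard to the reason for stopping: "participants who discontinued their medications were determined not adherent and those who continued were adherent".

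On stopping, Protocol 8.3.2 states "Metformin should be discontinued if the patient experiences a serious adverse event (SAE) that is thought to be related to the study drug", and also lets the treating clinician stop drug at discretion. Protocol 8.3.3 adds "For patients without side effects, dosing will continue daily for 90 days after the surgical encounter". Protocol 8.3.4 says that all patients receive drug for 90 days after surgery. The protocol's summary table words one secondary endpoint as "Gastrointestinal distress causing discontinuation of the medication", whereas SAP 9.2 records only whether intolerance was present.

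Neither document exempts these endpoints from the PPA, defines a separate safety population, or says which population supports a tolerability conclusion.

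**The concern.** PPA membership is settled at day 90, after the events have occurred and partly because of them. For an efficacy endpoint this is the usual weakness of a completers' analysis. For tolerability it is more direct, because the event itself is a reason for leaving the population in which it is counted.

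The matter is not peripheral here. SAP section 4 gives poor tolerance of study drug, alongside low enrolment, as a reason the trial ended, so readers will look for these results. They will find two sets of GI and SAE figures with equal standing, one of them depleted of the patients who could not tolerate the drug. The sensitivity analyses in SAP 13.2 repeat the comparison under three more definitions of treatment arm. If stopping after intolerance rises with dose, the PPA version would also flatten any gradient of intolerance by dose.

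**Working it through.** The plan states no rate or power for these endpoints, so there is no figure of its own to reproduce. The check has a textual part and an arithmetic part.

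**Text.** Event occurs (SAP 9.2) → drug is stopped, by the related-SAE rule or at discretion (Protocol 8.3.2) → patient is classed as not adherent (SAP 12) → patient is outside the PPA (SAP 8) → the PPA comparison is still made (SAP 11 and 13.2). No step has an exception.

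**Inputs.** The event rate g on metformin is 30–60%, the background range for GI discomfort in Protocol 6.2.3. The placebo rate (15%, varied from 10% to 20%) and all stopping probabilities s are assumptions, because the documents give none.

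**Formulas.** If patients stop only because of the event:

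- PPA rate = g(1 − s)/(1 − gs)
- PPA odds = [g/(1 − g)] × (1 − s)
- PPA OR = ITT OR × (1 − s_metformin)/(1 − s_placebo)

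Example: g = 0.45 and s = 0.5 give 0.225/0.775 = 29.0%. On placebo, g = 0.15 and s = 0.2 give 0.12/0.97 = 12.4%. The ITT OR is (0.45/0.55)/(0.15/0.85) = 4.64. The factor is 0.5/0.8 = 0.625, so the PPA OR is 2.90.

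| True rates, metformin v placebo | s, metformin v placebo | PPA rates | ITT OR | Factor | PPA OR |
|---|---|---|---|---|---|
| 45% v 15% | 0.5 v 0.5 | 29.0% v 8.1% | 4.64 | 1 | 4.64 |
| 45% v 15% | 0.5 v 0.2 | 29.0% v 12.4% | 4.64 | 0.625 | 2.90 |
| 30% v 15% | 0.5 v 0.2 | 17.6% v 12.4% | 2.43 | 0.625 | 1.52 |
| 60% v 15% | 0.5 v 0.2 | 42.9% v 12.4% | 8.50 | 0.625 | 5.31 |
| 30% v 15% | 0.7 v 0.2 | 11.4% v 12.4% | 2.43 | 0.375 | 0.91 |
| 45% v 15% | 0.2 v 0.5 | 39.6% v 8.1% | 4.64 | 1.6 | 7.42 |

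The factor does not depend on the placebo rate. At 45% on metformin with s of 0.5 v 0.2, a 10% placebo rate takes the OR from 7.36 to 4.60, and a 20% placebo rate takes it from 3.27 to 2.05.

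The first row separates the two effects. With equal stopping after the event the OR is unchanged, but both rates are too low and the risk difference falls from 30 points to 20.9. The last row shows that the OR bias can also run against metformin.

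**Stopping for other reasons.** If patients without the event stop with probability u, the PPA rate is g(1 − s)/[g(1 − s) + (1 − g)(1 − u)]. With g = 0.45, s = 0.5 and u = 0.2 this is 0.225/(0.225 + 0.44) = 33.8%. The understatement is smaller, and it remains as long as the event makes stopping more likely (s > u). A u that is equal in both arms cancels from the OR.

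**Drug-related SAEs.** Where Protocol 8.3.2 is followed, s is close to 1 in both arms, so few such events remain in the PPA. Under the protocol summary's GI wording, which builds discontinuation into the event, s equals 1 and the PPA count is zero by definition.

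**The case against.** The strongest reply is that the unselected comparison is already in the plan. The same sentence of SAP 13.2 runs every secondary endpoint in the ITT, SAP section 8 compares by allocated treatment, and stopping drug removes nobody from that population. SAP section 12 also has early terminations recorded and reported. Secondary endpoints are unadjusted and meant as context (SAP 13.6), and nothing says that a tolerability claim will rest on the PPA. All of this stands, and it confines the harm to the PPA output. It does not tell a reader which of the two results to rely on.

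Three stronger readings are tempting and should not be drawn.

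- A reader might infer from Protocol 8.3.3 that any side effect ends dosing, so that PPA intolerance would be zero in both arms. That sentence does not say so. Section 8.3.2 calls for stopping only after a related SAE and otherwise leaves it to discretion, and 8.3.4 has all patients dosed for 90 days. These passages need to be reconciled. Under SAP 9.2's present/absent definition, patients with GI intolerance who continue stay in the PPA.
- A reader might infer that a related-SAE model cannot be estimated. SAP 13.2 names no model for a graded endpoint. Also, "should" may not always be followed, and a bedside view of relatedness may differ from later adjudication. The supportable statement is that such events are largely removed.
- A reader might infer that the odds ratio is biased in metformin's favour by construction. That requires more stopping after the event on metformin. Treatment is blinded, Protocol 6.2.3 describes the GI effects as mild and self-limited, and no stopping rate is given. SAP section 4's remark on poor tolerance points the other way but carries no number.

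**Conclusion.** The point holds for the PPA output. Two results rest on the plan's own rules. PPA rates of GI intolerance are understated whenever intolerance makes stopping more likely (45% to 29% with half of the cases stopping and no other stopping). Drug-related SAEs are largely removed if Protocol 8.3.2 is followed.

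The effect on the odds ratio is conditional. It is nil with equal stopping after the event and no difference in other stopping. It favours metformin only if stopping after the event is more common on metformin. The shifts from 4.64 to 2.90, and from 2.43 to 1.52 or 0.91, illustrate assumed stopping rates and are not predictions; the reversal to 0.91 needs the most extreme of the gaps tried (70% v 20%). The ITT results are untouched by this selection. The gap to close is that the SAP gives both populations equal standing on a matter it names as a reason for closing the trial.

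**What to change.** In SAP 13.2, and in the matching statement in section 11:

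1. Omit GI intolerance and SAEs from the PPA analyses, including the alternative arm definitions in the 13.2 sensitivity analyses.
2. State that tolerability and safety conclusions rest on the comparison by allocated arm, whether or not drug was stopped.
3. Tabulate by arm the early terminations that SAP section 12 says coordinators already record.

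The GI endpoint wording in the protocol summary and in SAP 9.2 should be reconciled at the same time, so that the table states which event it counts.

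The cost is a few sentences of SAP text and the loss of a parallel PPA table. No new data are needed, fewer models are run, and no ITT figure changes.

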## 13. ANALYTIC APPROACH

Primary inferential analyses will be done using a Bayesian approach. Sensitivity analyses will be conducted using both Bayesian and Frequentist approaches, as described. Secondary endpoints will be analyzed using frequentist approaches. A summary of the analyses methods is provided below. For all frequentist models, statistical significance will be defined as a one-sided p-value of <0.025, and for all Bayesian models a one-sided posterior probability > 0.975. If stable inference cannot be made due to sparseness of data within strata/categories, data may be further collapsed as needed.

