### *Sensitivity Analysis*

Secondary endpoints will be assessed for alternative definitions of treatment arm. Analyses will mirror the primary analysis of secondary endpoints, replacing the treatment arm with the following alternative definitions:

1. Metformin 1500mg ER vs. Metformin 1000mg ER vs. Metformin 500mg ER vs. Placebo (each pooled across duration) (Primary Approach)
2. Long Metformin (>90 days) vs. Medium Metformin (29-90 days) vs. Short Metformin (7-28 days) vs. Placebo (each pooled across the 3 doses of study drug)
3. Placebo vs. 500mg and 7-28 day duration vs. all other treatment combinations

Model structures will mirror the primary analysis of secondary endpoints and statistical significance

will again be defined as an unadjusted  $p < 0.025$ .

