### **13.4. Exploratory Analyses**

Exploratory analyses after unblinding will not be considered inferential. Any *post hoc* exploratory analyses will be clearly labeled as exploratory and will use the conventions below.

1. Ordinal endpoints will be compared using a cumulative proportional odds model with summaries of the OR, 95% credible intervals, and Wilcoxon tests for robustness against a lack of proportional odds.
2. Time-to-Event analyses will utilize a Cox proportional hazards model, summarizing the hazard ratios and 95% confidence intervals.
3. Continuous endpoints will compare means with 95% confidence intervals based on two-sample t-test and/or Mann Whitney U test procedures.
4. Dichotomous proportions will be compared using logistic regression summarizing the OR and 95% confidence intervals. Differences between proportions will be summarized using observed differences and normal approximations for the 95% credible intervals.

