### **13.6. Multiple Comparisons**

No adjustment for multiple comparisons will be made, as the primary analysis model is for a single endpoint and secondary endpoints are intended to provide a broad statistical context for results of the primary analysis model.

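### SAP 13.2 declares secondary results statistically significant at an unadjusted p < 0.025 across about 270 overlapping fits, while 13.6 gives the same endpoints only a context role

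*SAP*

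**What the plan says.** - **Main secondary analysis (SAP 13.2, Primary Analysis).** Unadjusted linear, logistic and Cox models compare all metformin patients with placebo, "respectively on both the ITT and PPA populations". The decision rule is: "Statistical significance will be defined as an unadjusted" p < 0.025.
- **Further arm definitions (SAP 13.2, Sensitivity Analysis).** "Secondary endpoints will be assessed for alternative definitions of treatment arm": by dose, by preoperative duration, and by a split of the lowest dose with the shortest duration against all other combinations. Significance "will again be defined as an unadjusted" p < 0.025. The dose definition carries the tag Primary Approach, although the preceding subsection makes the pooled comparison the main one.
- **Sidedness (SAP 13).** "For all frequentist models, statistical significance will be defined as a one-sided p-value of <0.025". Section 13.2 does not restate a side or direction.
- **Multiplicity (SAP 13.6).** "No adjustment for multiple comparisons will be made"; the reasons given are that the primary model has one endpoint and that "secondary endpoints are intended to provide a broad statistical context for results of the primary analysis model".
- **Non-inferential label (SAP 13.4).** "Exploratory analyses after unblinding will not be considered inferential". The prespecified secondary endpoints are given no such label.

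No key secondary endpoint, testing order, gate or division of alpha appears anywhere in the SAP.

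**The concern.** Sections 13.2 and 13.6 pull in different directions. An endpoint that only gives context needs an estimate and an interval; it does not need a rule for declaring significance. As written, any secondary result below 0.025 may be reported as statistically significant, whichever endpoint, model form, arm definition or population produced it.

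This matters more here than in a completed trial. SAP section 4 says the trial stopped before its first interval analysis, planned at 500 patients, so an indecisive result on hospital-free days is plausible. A secondary result labelled significant (length of stay, readmission, ICU admission) could then draw attention that the plan did not intend for it.

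**Working it through.** The documents state neither a number of secondary tests nor a family-wise error rate, so there is no figure of theirs to reproduce. The per-test 0.025 is an input.

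**Step 1: count the fits.**
- Endpoint forms. SAP 9.2 lists 14 items. Four are categorical (SAE grade, discharge disposition, surgical site infection, surgical site occurrence), and 13.2 gives no model for them. The other 10 yield 15 modelled forms: 6 with one form each (gastrointestinal intolerance, ICU admission, ICU stay, hospital stay, in-hospital death, organ-failure-free days), reoperation with 3, and readmission, venous thromboembolism and mortality with 2 each. 6 + 3 + 2 + 2 + 2 = 15.
- Contrasts with placebo: 1 pooled + 3 doses + 3 durations + 2 for the combined split = 9.
- Populations: 2, with PPA nested in ITT.
- Total: 15 × 9 × 2 = 270. The designated analysis is 15 × 1 × 2 = 30; the sensitivity definitions are 15 × 8 × 2 = 240. If the Primary Approach tag is read as making the dose contrasts main as well, the main set becomes 15 × 4 × 2 = 120.

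**Step 2: upper reference, independent tests, no true effect.** The chance of at least one p below 0.025 in k tests is 1 − 0.975^k.
- k = 15: 0.316
- k = 30: 0.532
- k = 270: 0.9989, with 270 × 0.025 = 6.75 false positives expected

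The tests share patients, a placebo group and related endpoints, so these probabilities are too high.

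**Step 3: simulation with correlation.** From the documents: √3:1:1:1 allocation, the 9 overlapping contrasts, nested PPA, one-sided 0.025. Assumed, because the documents give no values:
- Model A: 10 normal endpoints (one form each), equal correlation 0.2 to 0.8, N = 150–500, duration mix 50/35/15%, a random 60% of patients in PPA, and contrasts with fewer than 10 patients skipped.
- Model B: all 15 forms, correlation 0 to 0.7, paired forms of one endpoint correlated 0.95 (independent in the zero-correlation case), duration mix 60/30/10%, PPA 40–80% of ITT.

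Chance of at least one false significant benefit:

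| Set of tests | Model A | Model B |
|---|---|---|
| Pooled contrast, ITT | 8–21% (about 15% at correlation 0.5) | 12–32% |
| Pooled contrast, ITT and PPA | not run | 16–48% |
| All 9 contrasts, ITT and PPA | about 40–77% (59–62% at correlation 0.5) | 50–95% |

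Over the nine ITT contrasts alone, model A gives about 45–49% at correlation 0.5. With a two-sided 0.025, model B gives 14–32% for the pooled ITT contrast and 65–97% for the full set, so the unstated side does not change the picture.

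**Step 4: what lowers these figures.** Protocol 11.2 lists gastrointestinal intolerance as a harm, so a false benefit there is unlikely. Deaths and thromboembolic events may be too rare for a test to reach its nominal level. If those four endpoints (gastrointestinal intolerance, in-hospital death, 90-day death, thromboembolism) contribute nothing, the full-set figure in model A falls to about 50% at correlation 0.5 and about 37% at 0.8.

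**The case against.** The strongest defence is that the plan is open about this. Section 13.6 declines adjustment and gives its reasons, section 13 reserves the primary inference for the Bayesian model, and the word unadjusted shows that the threshold is nominal. Section 13.2 also names one main contrast and asks for confidence intervals, so a p-value would not stand alone. All of this is fair, and it limits the point. It does not remove the conflict, because 13.2 still states in two places when a secondary result is to be called significant.

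Four stronger readings are tempting, and the documents do not support them:
- **A false secondary claim is more likely than not.** This does not hold for the designated pooled contrast. It passes one half only when the sensitivity definitions and PPA are counted as separate claims, and not under every assumption even then.
- **The error rate is many times the stated 0.025.** The SAP gives 0.025 as a per-test level and never offers it as a family-wise rate, so such a ratio compares unlike things.
- **The secondary endpoints are confirmatory because 13.4 calls only post hoc work non-inferential.** That is an inference from silence.
- **Secondary findings will carry the trial's message.** This predicts reporting behaviour, and the documents do not give the final enrolment.

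**Conclusion.** The point holds as an inconsistency between the significance rule in 13.2 and the context role in 13.6. The rule reaches about 270 overlapping fits, 240 of them headed as sensitivity analyses. The chance of at least one false significant benefit is about 8–21% for the pooled ITT contrast (12–32% with all 15 forms), and roughly 40–77% over all contrasts and both populations.

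These figures assume no effect on any endpoint, approximately normal test statistics, and the assumed correlations, sample sizes, duration mix and PPA fraction. Rare events, the rule in SAP section 11 against modelling groups under 10, and the known gastrointestinal harm would reduce them. The recommendation does not depend on the exact figure. The change is worth making because it settles what the trial may claim and leaves every analysis as it is.

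**What to change.** 1. Delete the significance sentence in both places in SAP 13.2.
2. State in 13.2 and 13.6: *Prespecified secondary endpoints are supportive. Effects are reported as estimates with 95% confidence intervals and, if shown, nominal p-values not adjusted for multiplicity. No statistical significance is claimed for any secondary endpoint under any arm definition or in either population.*
3. Limit the general frequentist threshold in section 13 in the same way, so that it does not bring the rule back for secondary endpoints.
4. Use the word supportive, not exploratory, because 13.4 uses the latter for post hoc work after unblinding.
5. Reconcile the Primary Approach tag on the dose definition with the pooled main contrast.

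The cost is SAP wording only; no model, data or estimate changes. The downside is that secondary results can no longer be called statistically significant. Section 5 places unblinding after SAP finalization, dated 06 September 2023. If unblinding has already taken place, the change is still safe as a reporting rule, because it only removes claims.
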